**10.4 Withdrawal by the physician:**

For clinical reasons not related to treatment.

**10.5 Violation of the study protocol:**

Including patient failure to return for required visits. Every effort should be made to contact such patients to determine their reason for withdrawal, and to assess any adverse events that may have contributed to the patient's failure to return. Patients who miss dose(s) because of holidays and/or clinic closures will not be withdrawn from the study.

**10.6 End of study**

Subjects in either cohort who do not meet any of the above criteria will be followed for 12 months after the completion of therapy (vaccination in the adjuvant cohort, Resiquimod in the metastatic cohort) and will be removed from the study thereafter.

## 11.0 Statistical Considerations

### Overview

This is a randomized phase II trial enrolling melanoma patients who are HLA-A2+ with or without HLA-DP4+. Patients of two separate types will be enrolled in separate cohorts. One cohort includes patients who are NED but at high risk for recurrence. The second cohort will include patients with non-visceral metastatic disease and must have at least two evaluable and biopsiable lesions to be eligible for the trial.

The trial will have two parts. In Part 1 (both cohorts), we will fairly randomize patients to receive either the gp100(g209-2M) +/-MAGE3 peptide vaccine plus a topical TLR 7 /8 agonist, R848, (Arm A) or the gp100(g209-2M) +/- MAGE3 vaccine alone Arm B). The randomization will be stratified by cohort. A total of 48 patients will be enrolled, 24 per arm. All patients will receive the gp100(g209-2M) vaccine (those who are HLA-DP4 + will also receive the MAGE3 vaccine) weekly (for 8 weeks) and the patients randomized to receive R848 gel will have the gel applied to the gp100(g209-2M) vaccine site weekly.

After 8 weeks of treatment on Part 1, Part 2 of the trial begins. In Part 2 (only patients in the metastatic disease cohort), the treating physician will divide the area of cutaneous lesions into regions, Region A and Region B and designate the two regions to receive or not to receive R848. At least one lesion will be randomly assigned to receive R848 from weeks 8 through 24, and one will not. One lesion from each region will be chosen for biopsy as outlined in section 7.3. If a patient has more than two evaluable lesions, we will stratify by lesion size to assure that the lesions will be comparable.

As a safety measure, if a patient's untreated lesions grow while treated lesions are stable or shrink, all lesions will be treated with R848. This will occur after the assessment of the primary endpoints of the study, so it will not affect the analysis of these endpoints.

In April 2015, the trial is being further modified to add an additional 20 patients with metastatic disease, all of whom will receive the the gp100(g209-2M) +/-MAGE3 peptide vaccine plus R848 (Arm C). These patients will not be part of the primary comparative study analysis of T-cell responses in the blood. The purpose of these patients is to provide additional information on characterizing tumor response, defined as at least a 50% shrinkage in tumor size by irRC criteria.

### Part 1

The primary objective of Part 1 of the trial is to compare T-cell responses in the blood between the vaccine+R848 and vaccine alone treatment arms. This will be assessed in the two cohorts separately and combined. The primary outcome of this part of the trial will be T-cell response to gp100(g209-2M) +/- MAGE3 measured at 8 weeks using a tetramer/multimer assay measured by flow cytometry. Based on the number of gp100(g209-2M) +/- MAGE3 T-cells measured, when the study began, patients were to be categorized as either immune responders or immune non-responders. From previous vaccine studies, a  $\geq 0.1\%$  response was thought to be a reasonable target. Thus, T-cell response to the gp100(g209-2M) + / - MAGE3 peptide in each patient was

defined as  $\geq 0.1\%$  gp100(g209-2M) tetramer+ cells in the CD8+ T-cell population or  $\geq 0.1\%$  MAGE3 multimer cells in the CD4+ T-cell population. In September 2013, due to problems in obtaining the multimers necessary to perform the CD4+ T-cell assays, these assays have not yet been run, although more than 24 patients have reached week 24 on the trial. Based upon the aggregate CD8+ responses, no patients have met the definition of response according to the above definition. Therefore, the study team is changing the definition of the primary endpoint to be the actual change from baseline for gp100(g209-2M) tetramer+ cells in the CD8+ T-cell population. The study will be stratified by cohort (NED/metastatic), but we expect the same immune response in each cohort.

For part 1 the 8-week primary immune outcome values CD8+ T-cell response will be compared between the two arms by using a Wilcoxon rank-sum test. Patients who discontinue from the study before week 8 will be assigned the lowest rank in this analysis. With one interim analysis, using an O'Brien-Fleming boundary to stop for efficacy, a one-sided significance level of 0.05, with 24 patients per arm, we will have 80% power to be able to detect an effect size of  $0.73^*SD(CD8+ T\text{-cell response})$ .

## Part 2

The primary outcomes for part 2 of the trial are immune cell infiltration for pDCs, mDCs, and NK cells in the tumor biopsy samples. This can be assessed in the metastatic disease cohort only, since those subjects in the adjuvant therapy cohort are free of disease. Tumor samples will be taken as outlined in section 7.3. Three different types of analyses will be performed on these tumor biopsies: (1) Immunohistochemistry (IHC) for the degree of pDC, mDC, and NK cell infiltration, (2) Flow cytometry (FACS) analysis for infiltrating melanoma specific CD8+ T cells, and (3) Quantitative RT-PCR (qRT-PCR) assays for IFN- $\gamma$ , IFN- $\alpha$  (and other type I interferons), IL-12, and TGF- $\beta$ . For each of these outcomes, we will determine the differences in each of these parameters between the pretreatment and post-treatment samples for each of the biopsied lesions for each patient. Mixed-effect models will be fit for each parameter to assess the effects of treatment, time, and the initial randomization to gp100(g209-2M) +/- MAGE-3 vs. gp100(g209-2M) +/- MAGE-3 +R848. If there is no evidence of an effect due to the initial randomization in Part 1, the changes from baseline for the R848 treated lesion and the untreated lesion will be calculated, and these differences will be compared between the R848 and non-R848 lesions by using a paired t-test.

A sample size argument for Part 2, based upon a 2-sample t-test (which represents a lower bound on the mixed-effects model given above), is as follows: we assume that a total of 24 patients will be enrolled in the metastatic disease cohort, and of these, 17% of the patients initially enrolled will discontinue the trial at 8 weeks due to progressive disease and that dropout will be equally distributed across the 2 arms, leaving a total of 20 patients (10/arm) for Part 2. The 2-sample t-test will assess differences in the change between the two treatment groups with respect to the 3 outcomes described previously. With 20 patients, we will have 80% power to detect an increase of 1.2 standard deviations in the R848 group for each outcome at 8 weeks, assuming a one-sided 2-sample t-test with a 5% Type I error rate. One of the benefits of our mixed-effects modeling approach is that it allows for the analysis of the data using complete likelihood methods (Beunckens, Molenberghs, and Kenward, 2005; Clinical Trials). In addition, we will perform 2 types of sensitivity analysis: 1) We will use last-observation-carried-forward; 2) We will explore how deviations from the Missing at Random (MAR)

assumption of the direct likelihood approach may impact inference using methods developed in Verbeke and Molenberghs (2000).

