infiltration, we plan to utilize this dose of R848 two times per week every 3-4 days (+/- 2 days), with the option of dose reducing from twice to once a week should patients experience any grade 3 or greater toxicity.

The physician will designate which of the two regions to receive or not to receive R848. (For example, if the cutaneous disease is limited to the thigh, the area of lesions will be divided in two with one region proximal and one region distal. Then the proximal region is assigned region A and the distal assigned region B. Resiquimod to be applied to region A or B. A 5mm margin will be included in the treatment area around each of the lesions at a spread rate of 10mcg/cm^2. The sum of the area of all treated lesions will not exceed 100cm^2. The treatment area will be allowed to air dry for 30 minutes and then covered with a gauze dressing which can be removed the following day. The R848 gel will be applied in the clinic by the research nurse for the first two weeks of administration, and then the subject will apply the gel at home thereafter. The patient will be trained for gel self-administration by the research staff. Sachets of gel will be supplied for home use and the subject will be instructed on maintaining a home record of administration. This home record or a progress note by one of the research team reviewing home administration may each act as a source document for all matters regarding home administration during this period. The gel may be applied in the clinic for longer than the first two weeks at the discretion of the investigators.

Tumor biopsies of treated and untreated lesions will be obtained as outlined in section 7.3 when feasible in order to assess T-cell infiltration and function at the site.

In order to give patients the opportunity to receive R848 gel on all their lesions, we will allow cross-over of patients who do not respond in untreated lesions by week 16 (8weeks after initiating gel on the tumors) in the untreated lesions to receive R848 gel on all of the lesions, but these patients will not be included in the final analysis of clinical endpoints that occur following week 24. Patients will not cross-over until after all blood, biopsies, and data are recovered for assessment of the primary endpoints in any subject. Treatment with R848 gel will continue for up to 4 months beyond week 24 as long as there is no disease progression.

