To evaluate the association between clinical response and laboratory parameters of T-cell priming, T-cell migration to tumor, and inflammation at the vaccine and tumor sites we will explore the relationship between immune cell activation measures at the vaccine site (vaccine site measures) and at the tumor site (tumor site measures). Additionally we will assess the effect of the TLR agonist R848 upon clinical response. Clinical response will be assessed using the immune-related response criteria (irRC) and will be assessed at week 8, 16, and every 8 weeks thereafter. Since both vaccine site measures and tumor site measures are continuous variables we will assess association between these two types of variables using Pearson's or Spearman's correlation coefficient. In addition, we will use logistic regression to model the relationship between either vaccine site or tumor measures and best clinical response assessed over a 16 weeks period after initial vaccination.

To assess the association between R848 treatment on lesions and response, the irRC will be used to assess response separately by lesion type (lesions receiving or not receiving R848 cream). That is, using the irRC, we will, for each patient, assess if the lesions not treated with R848 cream responded and also determine if the lesions treated with R848 cream responded. Thus, for each patient we will record 4 possible joint outcomes ++, +-, -+, and --, where the ++ indicates that both lesions receiving and not receiving R848 cream responded; -- indicates neither types of lesions responded. Similarly +- and -+ indicate one type of lesion responded while the other did not. We will assess differences between treatments (based on within patient differences) using McNemar's test. A statistically significant difference with respect to the McNemar's test will indicate if cream administered to the lesion results in improved outcome (i.e., immune-related response criteria) relative to lesions for which cream was not administered.

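### Two inconsistent crossover rules leave the paired lesion-response test open to counting R848-treated lesions as untreated

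*Combined protocol and SAP*

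**What the plan says.** In Part 2 (metastatic cohort) one region of lesions receives R848 and the other serves as the within-patient control. The Section 11.0 Overview describes the contrast: "At least one lesion will be randomly assigned to receive R848 from weeks 8 through 24, and one will not".

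Crossover of the control lesions is described twice.

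- **Section 6.0, Treatment Plan:** "we will allow cross-over of patients who do not respond in untreated lesions by week 16". This is a permission, and it does not depend on the treated lesions. Section 6.0 adds that "these patients will not be included in the final analysis of clinical endpoints that occur following week 24" and that "Patients will not cross-over until after all blood, biopsies, and data are recovered for assessment of the primary endpoints in any subject".
- **Section 11.0, Overview:** if a patient's "untreated lesions grow while treated lesions are stable or shrink, all lesions will be treated with R848". This is worded as mandatory. On timing it says only: "This will occur after the assessment of the primary endpoints of the study". It has no exclusion rule.

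Section 10.1 adds that progression found after the first ten weeks ends treatment.

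Under Overview of Analysis of Secondary Endpoints, each patient is classified by whether the treated and the untreated lesions responded under irRC, and then: "We will assess differences between treatments (based on within patient differences) using McNemar's test". No assessment week, window, significance level, sidedness or handling of crossed-over patients is given. The 16-week window in that section belongs to the logistic regression. Section 9.5 takes best response over the whole study from every assessment on record, and requires confirmation at least four weeks later.

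**The concern.** McNemar's test uses only the pairs in which one region responded and the other did not. Its validity depends on the untreated region staying untreated until it is scored. Crossover is triggered by failure of the untreated region, so it can reach a patient whose treated lesions alone responded, but never one whose untreated lesions alone responded. If lesions that later receive R848 still count as untreated, a treated-only responder can become a both-region responder. If crossed-over patients are dropped instead, the loss again falls on treated-only pairs and spares untreated-only pairs. What is at stake is the lesion-level evidence for objective 1.2.B.iv, the clinical response to R848 at the tumor site.

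**Working it through.** **1. The two triggers side by side.** Call a region responding (at least a 50% decrease, Section 9.4), growing, or stable (neither), with growth judged against the same baseline as response.

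| Treated | Untreated | Pair | Section 6.0 | Section 11.0 |
|---|---|---|---|---|
| response | response | both | no | no |
| response | stable | treated-only | yes | no |
| response | growth | treated-only | yes | yes |
| stable | response | untreated-only | no | no |
| stable | stable | neither | yes | no |
| stable | growth | neither | yes | yes |
| growth | response | untreated-only | no | no |
| growth | stable | neither | yes | no |
| growth | growth | neither | yes | no |

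Section 6.0 applies in 6 of 9 states and Section 11.0 in 2 of 9, both contained in the 6. Section 6.0 reaches every treated-only pair; Section 11.0 reaches only those whose untreated region is growing. Neither reaches an untreated-only pair. If the untreated region responds at 5% (borrowed from the standard-of-care ceiling quoted for Arm C, so an assumption), 100% − 5% = 95% of patients qualify under Section 6.0.

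The share of treated-only pairs reached by Section 11.0 was explored in a bivariate-normal model with assumed inputs: untreated response 5–10%, treated response 22–40%, untreated growth 30–70%, treated growth 0.6 times that, correlation 0–0.7. The share ran from 4% to 78%.

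**2. Timing.** Section 6.0 lets crossover start at week 16, which is 24 − 16 = 8 weeks before the stated end of the contrast. Section 11.0 names no week. The last Part 2 biopsy in Section 7.3 is at week 12, so on one reading its crossover could precede the week-16 response assessment. Responses are scheduled at weeks 8, 16 and every 8 weeks after that. A week-24 assessment therefore follows a week-16 crossover and is not after week 24. Confirmation of a week-16 response falls at 16 + 4 = week 20 or later, also after crossover may have begun.

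**3. Size.** The plan states no power for McNemar's test. The nearest stated figure is Arm A plus C, 30 patients, 5% against 22%: rejecting at 5 or more responses gives one-sided alpha 1.6% and power 82.1%, matching the stated 82%.

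For the paired test let a = P(treated-only), b = P(untreated-only) and n = pairs. The number of discordant pairs is D ~ Bin(n, a + b). Given D = d, treated-only pairs follow Bin(d, a/(a + b)), and the test rejects when the Bin(d, ½) upper tail is at most 0.05. Conversion of a share c of treated-only pairs replaces a by a(1 − c). At least five discordant pairs, all one way, are needed: 0.5⁵ = 0.031, whereas 0.5⁴ = 0.0625.

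The planned Part 2 numbers are 20 (Section 11.0) and at least 30 (Section 6.0). The rates, c and the one-sided 5% level are assumptions.

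| a, b | n | Power at c = 0 | Power at c > 0 |
|---|---|---|---|
| 0.30, 0.03 | 30 | 81% | 77% (5%), 73% (10%), 51% (30%), 26% (50%) |
| 0.30, 0.03 | 20 | 56% | 27% (30%), 11% (50%) |
| 0.19, 0.02 | 30 | 51% | 29% (25%), 9% (50%) |
| 0.19, 0.02 | 20 | 25% | 11% (25%), 3% (50%) |

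The second pair of rates matches 22% treated and 5% untreated response with 3% responding in both (0.22 − 0.03 = 0.19; 0.05 − 0.03 = 0.02). In the first row, expected discordant pairs fall from 30 × 0.33 = 9.9 to 30 × (0.15 + 0.03) = 5.4 at 50% conversion.

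**The case against.** Several points against the concern are sound.

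- **The plan has a partial safeguard.** Section 6.0 leaves crossed-over patients out of clinical endpoints after week 24. On the scheduled visits, a conversion first seen at week 24 would be confirmed at week 28 or later, arguably beyond the cut. This narrows the exposure but does not close it. The plan does not say whether a response is dated at first documentation or at confirmation, and the exclusion itself removes pairs in one direction.
- **The primary endpoints are protected.** Week-8 blood and week-12 biopsies come before any week-16 crossover, and both passages defer crossover until the primary endpoints are assessed. This stands.
- **The magnitude rests on unsupported inputs.** This also stands. A 30% treated-only rate exceeds the plan's 22% target, and no source supports 30% or 50% conversion, which would need lesions that had failed to respond, some of them growing, to shrink by at least half. Removal at progression (Section 10.1) may further limit crossover among patients with growing lesions.
- **The bias is toward the null** and the test may be underpowered in any case, so no false claim of efficacy follows. That limits the severity, but a planned comparison should still measure what it names.

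A reader might infer that the two rules are mutually exclusive, or that the Section 11.0 trigger removes exactly the discordant pairs. The documents do not support either reading. At week 16 the Section 11.0 condition is nested within that of Section 6.0. It also fires on a concordant pair (treated stable, untreated growing), misses treated-only pairs with a stable untreated region, and excludes nobody.

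**Conclusion.** The inconsistency is in the text. Sections 6.0 and 11.0 differ in who crosses over, whether crossover is optional, and when it happens. Either can cut short the week 8 to 24 comparator, and both need to be squared with removal at progression in Section 10.1. Followed as written, the plan lets McNemar's test count responses in lesions that are no longer untreated, and lets the post-week-24 exclusion drop treated-only but not untreated-only responders. Both push toward no difference. All treated-only pairs are exposed under Section 6.0, and only some under Section 11.0.

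The direction follows from the documents; the size does not. The illustration runs from a loss of a few points of power at 5–10% conversion to loss of most of it at 50%, all on assumed rates. The matter concerns one secondary analysis and leaves the primary endpoints intact, but it is worth correcting because the repair is cheap.

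**What to change.** 1. Reconcile the crossover passages in Sections 6.0 and 11.0 with each other, with the stated week 8 to 24 contrast, and with Section 10.1. Which clinical rule applies is for the investigators to decide.
2. For McNemar's test, classify both regions at one common assessment for all patients that precedes any crossover. The scheduled week-16 assessment serves if the reconciled rule permits no earlier crossover.
3. State that an untreated region is never scored from assessments made after it has received R848, and that confirmation of a treated-region response may come later.
4. Keep crossed-over patients in the paired analysis with that classification.

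A common time is preferable to cutting each patient at their own crossover. An individual cut would make length of follow-up depend on outcome and, read literally, would block the four-week confirmation of a week-16 response.

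The cost is protocol and SAP wording, plus shorter follow-up in the paired comparison: responses arising after the common assessment are not counted there.

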### **6.0 Treatment Plan**

All patients will receive the class I, HLA-A2 restricted gp100(g209-2M) peptide vaccine. Patients who are HLA-DP4 positive will also receive the class II restricted MAGE-3 peptide, in separate extremities. This will allow us to generate melanoma-specific CD8+ and CD4+ T-cells. The gp100(g209-2M) immune response will be our primary endpoint for assessment of T-cell priming, since we have extensive previous experience with this vaccine and believe that CD8+ responses are critical to the development of a strong antitumor immune response. The MAGE-3 peptide will be given in order to stimulate antigen-specific CD4+ T-cells, which we believe are also important in the generation of strong antitumor immunity. Patients positive for both HLA types will

receive both vaccines, gp100(g209-2M) and MAGE-3, for eight weeks. Patients who are HLA-A2 positive and HLA-DP4 negative will receive only the gp100 peptide for 8 weeks. There will be two arms in Part 1: Arm A is the peptide vaccines plus the TLR7/8 agonist, R848 and Arm B is the peptide vaccines only. All patients will be randomized to either Arm A or Arm B by CORe during the registration process. The randomization will be stratified by cohort (metastatic disease or adjuvant). In Arm A, R848 gel will be applied to the gp100(g209-2M) vaccine injection site immediately following the injection. The R848 gel will be allowed to air dry for 30 minutes and then covered with a gauze dressing. All vaccines will be administered subcutaneously and intradermally. The gp100(g209-2M) peptide will be administered in the same extremity weekly (every 7 days +/- 2 days) for 8 weeks. Similarly, in a separate extremity of eligible patients, the MAGE-3 peptide will be administered weekly (every 7 days +/- 2 days) for 8 weeks. Each syringe (a total of 4, 2 for gp100 and 2 for MAGE-3) will contain 1ml of peptide vaccine; 0.5ml of the vaccine in each syringe will be administered intradermally and the other 0.5ml will be administered subcutaneously at each injection site for a total of 4 sites.

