## Study Stopping Criteria

We will conduct an interim analysis after half of the patients have been enrolled and have reached week 8 on the study. At the interim analysis, we will test whether there is strong evidence that the immune responses differ between the two treatment arms. We will use an O'Brien-Fleming stopping boundary to stop for efficacy, with a nominal significance level of 0.0056. With the alpha spent at the interim look, the nominal significance level at the final analysis will be 0.0482.

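### The Part 1 primary Wilcoxon test uses the week-0 tetramer level only by subtraction and leaves out the cohort stratum; a prespecified rank-based adjustment is a cheap improvement of uncertain size

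*Combined protocol and SAP*

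**What the plan says.** Section 11.0, Part 1, redefines the primary endpoint as "the actual change from baseline for gp100(g209-2M) tetramer+ cells in the CD8+ T-cell population". The week-8 values "will be compared between the two arms by using a Wilcoxon rank-sum test". Patients who leave before week 8 take the lowest rank. No baseline covariate is named.

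Section 6.0 says: "The randomization will be stratified by cohort (metastatic disease or adjuvant"), and the Section 11.0 Overview repeats this. Part 1 adds that the comparison is made within each cohort and overall, that the study is stratified by cohort, and that the same immune response is expected in both. It does not give a stratified form of the combined test.

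On size, the Overview states "A total of 48 patients will be enrolled, 24 per arm". Part 1 assumes "a one-sided significance level of 0.05, with 24 patients per arm", and says "we will have 80% power to be able to detect an effect size of" 0.73 SD of the CD8+ response. Study Stopping Criteria sets one O'Brien-Fleming look at half the patients "with a nominal significance level of 0.0056", after which "the nominal significance level at the final analysis will be 0.0482".

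Sections 6.0 and 7.2 schedule blood collection at week 0 and week 8 in both cohorts, so the baseline value exists for every patient who has a change score.

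**The concern.** A change score is the week-8 value minus 1 times the week-0 value. The slope that minimises the residual variance is rho/k, where rho is the week-0 to week-8 correlation and k = SD(week 0)/SD(week 8). Unless rho equals k, the change stays correlated with baseline. A chance imbalance in week-0 levels then shifts the arm comparison, and some removable variance stays in the outcome. With 24 patients per arm, that could cost power.

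Randomisation is balanced within cohort, but a plain rank-sum test does not use that balance. If the cohorts differ in change, the difference stays in the error term.

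At stake is the precision of the primary comparison. Its validity is not in question.

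**Working it through.** **Inputs from the documents.** 24 per arm; effect 0.73 SD, read as the SD of the change; one-sided 0.05; nominal levels 0.0056 (interim, half information) and 0.0482 (final). The documents give no rho, no k and no Part 1 discontinuation rate, so these are assumptions shown as ranges.

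**Step 1: the plan's power.**
- Normal formula: Φ(0.73 × √(24/2) − 1.645) = Φ(2.529 − 1.645) = Φ(0.884) ≈ 81.2%.
- Noncentral t at one-sided 0.05: 80.1%.
- Two looks at 0.0056 and 0.0482: 80.9%, or 79.3% with the Wilcoxon efficiency 3/π. The two levels together spend 0.04997.
- Simulated Wilcoxon on normal data: 77.9% with two looks, 78.4% in a fixed design at 0.05.

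The stated 80% is therefore about right for the unadjusted test.

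**Step 2: variance after adjustment.** With the week-8 SD set to 1, the change has variance 1 + k² − 2·rho·k, and the baseline-adjusted residual has variance 1 − rho². The ratio, adjusted over change, is

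(1 − rho²) / (1 + k² − 2·rho·k).

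At k = 1 it reduces to (1 + rho)/2. At rho = k it is exactly 1, so nothing is gained. Examples:
- rho 0.2, k 1: 0.96/1.60 = 0.60
- rho 0.5, k 0.5: 0.75/0.75 = 1.00
- rho 0.2, k 0.25: 0.96/0.9625 = 0.997
- rho 0.8, k 0.25: 0.36/0.6625 = 0.543

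**Step 3: simulated power of the proposed test.** Ranked change is regressed on arm, ranked baseline and cohort. Settings: normal data, 24 per arm, 0.73 SD of change, fixed design, one-sided 0.05, no dropout, 4,000 runs (standard error about √(0.78 × 0.22/4000) = 0.65 points).

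| k | rho | Variance ratio | Plain Wilcoxon | Rank ANCOVA |
|---|---|---|---|---|
| 1 | 0.2 | 0.60 | 79% | 93% |
| 1 | 0.5 | 0.75 | 78% | 87% |
| 1 | 0.8 | 0.90 | 78% | 81% |
| 0.5 | 0.2 | 0.914 | 79% | 82% |
| 0.5 | 0.5 | 1.00 | 78% | 78% |
| 0.5 | 0.8 | 0.80 | 77% | 85% |
| 0.25 | 0.2 | 0.997 | 78% | 78% |
| 0.25 | 0.5 | 0.923 | 79% | 81% |
| 0.25 | 0.8 | 0.543 | 77% | 94% |

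Repeat runs move these figures by 1 to 2 points; for example, 91% to 93% in the first row. In 6,000 runs near rho = k, the adjusted test was slightly behind: 79.0% against 77.6% (rho 0.5, k 0.5), 79.2% against 77.8% (rho 0.2, k 0.25) and 77.5% against 76.7% (rho 0.1, k 0.1). Lognormal data with equal SDs on the log scale gave smaller gains: 81% to 88%, 79% to 82% and 74% to 75% at rho 0.2, 0.5 and 0.8. Type I error of the adjusted test stayed between 4.6% and 5.4%.

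**Step 4: with the lowest-rank rule in force.** Baseline cannot explain the bottom ranks given to discontinuations, so the gain shrinks. With an assumed 10% discontinuing in each arm, plain Wilcoxon power is about 61% and adjusted power about 60% to 72%. With an assumed 17% (the plan's figure for the metastatic cohort in Part 2) and k = 1, power goes from 50.5% to 56.1%, from 49.5% to 52.7% and from 49.7% to 50.1% at rho 0.2, 0.5 and 0.8.

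**The case against.** The strongest reply is that the planned test is sound. In a randomised comparison a Wilcoxon on change controls type I error, needs no normality and takes the discontinuation rule directly. It reaches about its stated power. The benefit of adjustment rests on two quantities that nobody has documented, and the primary endpoint has already been redefined once, after more than 24 patients had reached week 24. All of this stands. It limits the point to an improvement and requires that any change be fixed without sight of arm-level results.

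Two further objections do not stand. An ordinary ANCOVA would need an extra rule for discontinuations, but a rank-based one keeps the lowest-rank rule as written. And a comparison made within cohorts and overall does not make the combined test a stratified one.

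A reader might also draw stronger conclusions, which the documents do not support:
- *That the week-0 level is thrown away.* It is subtracted. Only the gain from estimating its slope, instead of fixing it at 1, is forgone.
- *That power is certainly lost, and without any return.* The loss is zero at rho = k, and the plain test buys simplicity and robustness.
- *That adjustment can only help.* With 48 patients the extra parameters can cost about 1 point.
- *That values near the assay floor make baseline correlation low, and that this is where adjustment helps most.* The plan reports only that no patient met the 0.1% response definition. Low rho brings a large gain only if k is near 1. If baseline values are bunched and week-8 values spread out, k is small as well and the gain disappears.

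**Conclusion.** The point holds as a cheap improvement. The primary test is a plain Wilcoxon on change that fixes the baseline slope at 1 and, as written, leaves out the randomisation stratum. For rho from 0.2 to 0.8 and k from 0.25 to 1, with no dropout, adjustment takes power from about 78% to between about 77% and 93% (94% in one scenario). With 10% discontinuing it goes from about 61% to about 60–72%.

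These figures assume a 0.73 SD effect on the change scale, a fixed one-sided 0.05 test and normal data. Discontinuation, where assumed, is equal in the two arms. Skewed data gave smaller gains. The range is not a bound, because rho and k are unknown. Neither the validity of the planned test nor the plan's 80% figure is challenged.

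**What to change.** Before any further unblinded analysis, amend Section 11.0, Part 1:

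1. State that the tested value is the week-8 change. The present description of 8-week outcome values could also be read as the raw week-8 level.
2. Make the primary test a rank-based ANCOVA. Rank the week-8 change over both arms, with discontinuations before week 8 keeping the lowest rank. Regress the ranks on arm, ranked week-0 tetramer percentage and cohort. Test arm one-sided at the existing nominal levels, 0.0056 and 0.0482.
3. For the within-cohort analyses, use the same model without the cohort term.
4. Keep the plain Wilcoxon as a sensitivity analysis.

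The documents do not say whether the interim analysis has been done. If it was done with the plain Wilcoxon, record that and apply the change to the final analysis only. Total one-sided error then cannot exceed the sum of the two nominal levels, 0.0056 + 0.0482 = 0.0538, if each test holds its level.

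The cost is an amendment to the statistical section and a few lines of code, with no new data. The price is a possible loss of about 1 point of power when rho is near k, and one more change to the primary analysis, to be documented as made blind to arm-level results.
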